# 7.4. Randomising on the day of surgery

Recruiting centres will be asked to randomise participants on the day of surgery, once the planned surgery is confirmed as taking place. There will be occasions when surgery is cancelled at the last minute and rescheduled to another day. If the participant is happy to remain in the trial, recruiting centres will be asked to inform the GlucoVITAL team of the new surgery date as soon as possible, and data collection timepoints will be adjusted. Participants should receive their original allocated intervention at their new scheduled surgery date. If the surgery is cancelled indefinitely, or the participant is no longer suitable for the trial, the recruiting centre will be asked to inform the GlucoVITAL team as soon as possible.

#### 7.5. Trial intervention

Anaesthesia will be administered by experienced anaesthetists and delivered according to local guidelines. All other participant care will be conducted as per routine clinical practice. More detailed information regarding trial intervention will be provided to sites as part of the trial-specific training.

#### 7.5.1. Total Intravenous Anaesthesia (TIVA)

Participants randomised to the TIVA arm of the trial will have their maintenance of anaesthesia performed with intravenous anaesthetic agents as determined by the treating anaesthetist. Administration of TIVA will not be protocolised and will be left to clinical discretion for management. Maintenance of general anaesthesia should be via TIVA only. During training, it will be emphasised that clinicians should not expose TIVA group participants to inhaled anaesthetic agents.

#### 7.5.2. Volatile-based Inhalational Anaesthesia (INH)

Participants randomised to the INH arm of the trial will have their maintenance of anaesthesia performed with inhalational volatile-based anaesthetic agents as

determined by the treating anaesthetist. Administration of INH will not be protocolised and will be left to clinical discretion for management. Maintenance of general anaesthesia should be via inhalational route only. During training, it will be emphasised that clinicians should not expose INH group participants to intravenous anaesthetic agents.

#### 7.6. Glucose measurements

Glucose will be measured using:

- Blood-gas measurements recorded on:
  - Day of surgery before induction of anaesthesia
  - End of surgery defined as the patient leaving the operating room (+ 2 hours)
  - Day one after surgery (10:00am ± 6 hours)
- Continuous glucose monitoring Dexcom G7 patches and sensor. The patient
  will wear these monitors continuously from induction of anaesthesia up to 10
  days postoperatively [maximum usage duration for each sensor] or hospital
  discharge whichever occurs sooner. The glucose monitor will be provided by
  the Sponsor.

#### 7.7. Assessment of outcome measures

Blood samples (approximately 15 ml) will be collected to measure:

- Myocardial injury: Plasma high sensitivity troponin-T (Elecsys, Roche Diagnostics) levels will be measured in blood samples collected on the day of surgery before the induction of anaesthesia and on day one after surgery (10:00am ± 6 hours).
- Presence and/or development of insulin resistance: Plasma C-peptide and insulin levels (ELISA assays) will be measured on the day of surgery before the induction of anaesthesia and on day one after surgery (10:00am ± 6 hours).
- Leukocyte and metabolic profiles: Whole blood will be analysed by flow
  cytometry on the day of surgery before the induction of anaesthesia, within 2
  hours after the end of surgery (defined as time at which surgical drapes are
  removed), day one after surgery (10:00am ± 6 hours) and day of hospital
  discharge (10:00am ± 6 hours). This will only be done at selected sites.

Participants will be contacted by telephone at day 30 (+ 7 days) by site research staff to collect data on hospital readmission and any postoperative complications that classed as Clavien-Dindo Severity Grade II or above (Appendix A). When assessing the Clavien-Dindo complications, if the initial assessment will be made by a research associate; this will typically be a research nurse but may include physicians and surgeons. This initial assessment by the research associate will be based on clinical information including information from patients' medical notes, including (but not limited to) microbiology test results, blood test results, drug prescription charts, radiology tests etc. Patients discharged from hospital before day 30 will be contacted shortly after day 30 to ascertain whether they have received any new treatment since discharge, or if they have been re-admitted to hospital or seen a doctor since discharge. For patients who have received further treatment or seen a health professional since discharge, further details will be collected directly from the hospital/doctor or from the patient's health records to be used in the research associate's assessment. If the initial assessment by the research associate is of 'no infection', then the patient's outcome is classified as 'no infection'. If the initial assessment is of 'infection', then this decision must be confirmed by the site Principal Investigator (PI), who will evaluate the information used by the research associate in their initial assessment. The Pl's decision is final; they can either confirm the research associate's initial assessment of 'infection' (in which case the patient's outcome is classified as 'infection'), or they can refute it (in which case the patient's outcome is classified as 'no infection').

# 7.8. Schedule of study intervention

Visit	Day 0 pre-op	Day 0 post-op	3 Day 1 # post-op	4 Day 2- Day10 post-op	5 Day of hospital discharge#	6 Day 30 + 7 days
Visit Window						
Informed consent	х					
Medical history	х					
Inclusion/exclusion criteria	х					
Surgical speciality	х					
Expected duration of surgery (<2hrs, ≥2hrs)	х					
Cancer surgery/non-cancer surgery	х					
Preoperative frailty (Rockwood Frailty Score)	х					

Collection of trial blood sample	Х	Х	х		X*	
Blood gas glucose measurement	х	х	х			
Real time continuous glucose monitoring	х	х	х	х		
Post-operative complications (Clavien-Dindo Grade II and above)						х
Length of stay					х	
Survival status						х
Hospital readmission						х

\* Or closest next working day

# 7.9. Written/ reading / translation considerations

The research team will not recruit participants unless the patient information sheet, consent form and video are provided in the appropriate language.

#### 7.10. Withdrawals

Participants may withdraw from trial at any time without prejudice. Data will be collected as per the trial protocol unless the participant has explicitly withdrawn their consent.

#### 7.11. End of trial definition

The end of the trial (EOT) is defined as 180 days from the when the last patient had completed their 30 day follow-up.

# 8. Laboratories and samples

# 8.1. Central laboratories

Myocardial injury will be assessed based on plasma high sensitivity troponin-T (Elecsys, Roche Diagnostics) and the analysis will be conducted by The Doctor's Laboratory.

#### 8.2. Local laboratories

C-peptide analysis and insulin resistance will be measured on plasma samples (using validated enzyme-linked immunoassays) and the analysis will be conducted

\* This will only be done at selected sites.

by the Chief Investigator (CI) in the Translational Medicine and Therapeutics laboratory, William Harvey Research Institute (WHRI).

# 8.3. Sample collection and labelling logging

All blood samples will be pseudo-anonymised. Samples collected at each participating site will be labelled with the participant's corresponding study ID and kept in a hospital freezer at an optimal temperature for the troponin assay until collection. The samples will be routinely collected and transferred to WHRI where they will be stored prior to transfer to The Doctor's Laboratory for analysis. The full sample, collection, labelling, logging and transfer procedure will be documented in the trial laboratory log.

# 8.4. Sample receipt/chain of custody/accountability

Handling of the samples upon arrival at the local and central laboratory will be documented. All samples will be logged upon receipt and the laboratory will ensure that the integrity of these samples have not been compromised in transit. If compromise has occurred, the trial coordinating team, as well as the Sponsor, will be informed of this. Upon receipt of samples, laboratory staff will ensure that all samples are accounted for as per the labelling.

#### 8.5. Sample storage procedures

The samples should be put in the freezer within two hours of blood samples being collected from the patient. The samples will not be destroyed if a patient withdraws from the study unless they specifically request so. If the patient requests for the samples to be destroyed the Tissue Custodian (CI), will inform the lab who will ensure the samples are destructed as per the Human Tissue Act. This will be documented in the Trial Master File and Investigator Site File of the participating site.

#### 8.6. Sample and data recording/reporting

Troponin-T data will be measured by the central laboratory and shared by secure electronic communication after the last patient sample has been analysed.

#### 8.7. End of study

The samples will be stored beyond the end of the trial to be used for closely related studies in the future. After completion of any potential sub-studies the samples will be destroyed according to the Human Tissue Authority's Code of Practice.

# 9. Safety reporting

#### 9.1. Definitions

#### 9.1.1 Adverse Events (AE)

An Adverse Event (AE) is defined as any untoward medical occurrence in a trial participant, and which does not necessarily have a causal relationship with the treatment/intervention.

### 9.1.2 Serious Adverse Events (SAEs)

A Serious Adverse Event is an AE that fulfils one or more of the following criteria:

- Results in death
- Is immediately life-threatening
- Requires hospitalisation or prolongation of existing hospitalisation
- Results in persistent or significant disability or incapacity
- Is a congenital abnormality or birth defect
- Immediate intervention was required to prevent one of the above or is an important medical condition.

#### 9.2 Site investigator assessment

The Principal Investigator is responsible for the care of the participant, or in their absence an authorised medic within the research team is responsible for assessment of any event for:

- Seriousness: Assessing whether the event is serious according to the definitions given in section 9.1.
- Causality: Assessing the causality of all serious adverse events in relation to the study treatment according to the definition given. If the SAE is assessed as having a reasonable causal relationship with the investigational device, then it is defined as an ADE.
- Expectedness: Assessing the expectedness of all ADEs according to the definition given. If the ADE is unexpected (as per the risk analysis or other RSI document), then it is a USADE.
- Severity: Assessing the severity of the event according to the following terms and assessments. The intensity of an event should not be confused with the term "serious" which is a regulatory definition based on participant/event endpoint criteria.

o Mild: Some discomfort noted but without disruption of daily life

- o Moderate: Discomfort enough to affect/reduce normal activity
- o Severe: Complete inability to perform daily activities and lead a normal life

It is expected that patients undergoing major abdominal surgery will suffer medical complications, with consequences up to and including death. Only complications considered by the CI to be related to the use of study procedures and not a typical complication of surgery should be reported as SAEs.

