#### 9.2.1 Notification and reporting of Serious Adverse Events

Serious Adverse Event (SAEs) that are considered to be 'related' and 'unexpected' are to be reported to the sponsor and the sponsor's representative for that country within 72 hours of learning of the event.

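### Protocol sections 9.2 to 9.2.2 conflict on who judges an SAE related, what it must be related to, and which SAEs sites must report

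*Protocol*

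**What the plan says.** Section 9.2 is headed as the site investigator's assessment. It places the duty on the PI; in the PI's absence, "an authorised medic within the research team is responsible for assessment of any event for" seriousness, causality, expectedness and severity. On causality it asks for "Causality: Assessing the causality of all serious adverse events in relation to the study treatment according to the definition given". The next sentence changes the reference: "If the SAE is assessed as having a reasonable causal relationship with the investigational device, then it is defined as an ADE". Expectedness is then confined to that class of event: "Assessing the expectedness of all ADEs according to the definition given", and "If the ADE is unexpected (as per the risk analysis or other RSI document), then it is a USADE".

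The section ends with an exemption for the complications expected after surgery. It limits SAE reports to one class of event: "Only complications considered by the CI to be related to the use of study procedures and not a typical complication of surgery".

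Section 9.2.1 says that SAEs "that are considered to be 'related' and 'unexpected' are to be reported to the sponsor" within 72 hours. It names neither an assessor nor a device. Section 9.2.2 tells sites to notify their co-ordinating centre of an SAE within 72 hours and repeats neither condition.

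Elsewhere, sections 4.3 and 7.3 make clear that the randomised comparison is TIVA against inhalational anaesthesia. Section 7.6 describes the one device supplied for participants, a continuous glucose sensor used for measurement in the trial as a whole.

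**The concern.** A site needs three things from these sections: who decides that an event is related, related to what, and which events then have to be sent. On each of them the text gives more than one answer. The device wording matters because the expectedness step depends on it, and section 9.2.1 uses expectedness as one of its two reporting conditions.

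What is at stake is consistent expedited reporting. Under section 14.3 the DMC reviews safety data by randomised arm. So far as that review draws on SAE reports, differences between sites in what they send weaken it. Omissions are also unlikely to be noticed: section 13.6 rules out routine monitoring and source data verification, and section 11.1 marks annual safety reporting as not applicable.

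**Working it through.** No figure is involved, so the check is to set the rules side by side and follow an event through them.

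| Place | Who judges | Causal reference | Condition for reporting |
|---|---|---|---|
| 9.2, causality, first sentence | PI or authorised medic | Study treatment | None stated |
| 9.2, causality, second sentence | PI or authorised medic | Investigational device | None; labels the event an ADE |
| 9.2, expectedness | PI or authorised medic | ADEs only | None; labels the event a USADE |
| 9.2, closing sentence | CI | Study procedures | Related, and not typical of surgery |
| 9.2.1 | Not named | Not named | Related and unexpected |
| 9.2.2 | Site sends the report | Not named | None stated |

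**An SAE that the PI attributes to the allocated anaesthetic.**

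1. Under the first causality sentence it is related, taking study treatment to mean mode of anaesthesia.
2. Under the second sentence it is not an ADE, because an anaesthetic technique is not a device.
3. Expectedness is required only for ADEs, so section 9.2 does not ask for it here.
4. Under the closing sentence it counts only if the CI considers it related to study procedures and not typical of surgery. Whether the allocated anaesthetic is a study procedure is not stated, and no route is described by which the CI forms a view before the site reports.
5. Section 9.2.1 needs the event to be both related and unexpected. The first was answered at step 1; the second was not asked for at step 3.
6. Under section 9.2.2, read alone, the site reports it within 72 hours.

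Three sites acting in good faith could therefore report it, wait for the CI, or leave it unsent because no expectedness assessment was made.

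**An SAE attributed to the glucose sensor.** If the sensor is the investigational device, which the protocol does not say, the event is an ADE, gets an expectedness assessment and can become a USADE. The pathway is thus complete for the component that is not randomised and incomplete for the one that is.

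**Definitions.** Section 9.2 points to a given definition for both causality and expectedness. Section 9.1 defines only AE and SAE, and neither of the other two definitions appears in section 9. ADE, USADE and RSI are expanded neither there nor in the glossary, and the document against which expectedness is judged is left open.

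**Population.** The exemption speaks of major abdominal surgery. Section 6.2 admits elective major noncardiac surgery generally, and section 7.3 lists musculoskeletal, thoracic and vascular specialties among others.

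**The case against.** The best defence is that the device terms look like leftover template text and that the rest can be worked with. Much of this stands, and it rules out several stronger readings.

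- A reader might infer that an anaesthesia-related SAE can never qualify for reporting. The text does not support that. Section 9.2.1 does not depend on the ADE or USADE labels, the first causality sentence refers to study treatment, and nothing bars a PI from calling such an event unexpected.
- A reader might take the closing sentence of 9.2 as the only rule telling sites what to send. Sections 9.2.1 and 9.2.2 also instruct them. Section 9.2.2 may be meant only as the procedure for events already found reportable, but it does not say so.
- A reader might call the CI condition circular, on the ground that the CI sees an event only after it is reported. That is an inference. Section 14.1 puts day-to-day conduct under the CI's management, and nothing prevents a site from consulting the CI first. What the text shows is two assessors for one judgement.
- The device wording is not baseless. The sponsor supplies the sensor, and sensor readings are a secondary outcome. The wording is incomplete rather than irrelevant.
- Events are not wholly lost. Sections 7.7 and 7.8 collect complications of Clavien-Dindo grade II or above, survival and readmission at day 30. The DMC's remit is safety data, not SAE forms alone. These data come later than 72 hours, however, and no causality assessment is described for them.
- Exempting typical surgical complications is a legitimate choice when two usual-care techniques are compared, and is not challenged here.

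None of this removes the conflict. Usual-care arms can justify light reporting, but not rules that sites cannot all follow at once.

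**Conclusion.** The point holds as an internal inconsistency in operative safety rules. Section 9.2 names two assessors of relatedness and three causal references, and limits expectedness to device-related events in a trial that randomises mode of anaesthesia. Sections 9.2, 9.2.1 and 9.2.2 word the reporting condition in three ways. Sites may differ in what they send, and an SAE related to the allocated anaesthetic may miss 72-hour reporting. That outcome is possible rather than certain, and the protocol gives no basis for estimating how many events it would affect.

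This rests on three assumptions: that study treatment means the allocated mode of anaesthesia; that the sensor is the only candidate for the investigational device; and, for the effect on by-arm review, that the DMC's safety data include SAE reports, which section 14.3 does not specify. The correction should be made, because it is cheap and concerns rules that sites have to apply.

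**What to change.** Reconcile sections 9.2, 9.2.1 and 9.2.2:

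1. Name one assessor of relatedness at the time of reporting. The text already gives this to the site PI or authorised medic. State how the CI's view relates to that assessment.
2. Define relatedness and expectedness against the study intervention (mode of anaesthesia) and study procedures, naming the glucose sensor among the latter. Use these in place of the investigational device, ADE and USADE terms, supply the two missing definitions, and name the reference document for expectedness.
3. State one reporting condition and use the same words in all three sections.
4. Keep the exemption for typical surgical complications, but make its population match the eligible one, major noncardiac surgery.

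The cost is protocol wording. Sample size, visits and outcome data do not change. Any effect on the number of SAE forms cannot be derived from the protocol.

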#### 9.2.1 Notification and reporting of Serious Adverse Events

Serious Adverse Event (SAEs) that are considered to be 'related' and 'unexpected' are to be reported to the sponsor and the sponsor's representative for that country within 72 hours of learning of the event.

# 9.2.2 Reporting a Serious Adverse Events

Individual sites will notify the co-ordinating centre in that country of an SAE by emailing a scanned copy of the supplementary SAE report form to the national coordinator. SAEs will be reported within 72 hours and will be forwarded to the sponsor via the UK co-ordinating centre.

#### 10. Statistical considerations

A detailed statistical analysis plan will be drafted by the trial statistician, which will be finalised and approved by the CI and an independent statistician before the final data analysis. All statistical analyses will be undertaken on an intention to treat basis to preserve randomisation, avoid bias from exclusions and preserve statistical power. Hence all participants enrolled into the study, regardless of whether they received their randomised intervention, will be analysed according to their randomised group using data collected up to their 30-day time-point, or the last time-point prior to their withdrawal or loss to follow-up before this. Patients not receiving surgery or withdrawing consent for follow-up prior to surgery will not be included in relevant denominators.

For the primary outcome of blood glucose change from the start of surgery until the end of surgery, each randomised treatment arm's point estimates (and 95% confidence interval) will be reported. In addition, blood glucose measurements from the start of surgery until the end of surgery will be compared across randomised

treatment arms using independent samples t-tests, or Wilcoxon rank sum tests depending on the distribution of the data. The secondary clinical outcomes (incidence of myocardial injury and/or all-cause infection) will be assessed across trial arms using a chi-squared test. The continuous variables measuring mechanistic outcomes of glucose and metabolic profiles will initially be compared across trial arms using independent samples t-tests, or Wilcoxon rank sum tests (depending on the distribution of the data). Further comparisons across trial arms of blood glucose measures over time and the mechanistic outcomes over time will use repeated measures analyses, a statistically efficient approach that allows all of the follow-up data collated during the study to be used.

For GlucoVITAL, four factors define sub-groups of interest: (1) Surgical speciality (intrabdominal/other); (2) Cancer surgery/non-cancer surgery; (3) Incidence of hyperglycaemia (glucose <7.8mmol/L) within first 24h of surgery (including at time of induction of anaesthesia); (4) Diabetes mellitus/no diabetes mellitus. Pre-specified sub-group analyses that will be undertaken using appropriate modelling techniques. These will be determined following examination of the distributions of the collected data. These exploratory sub-group analyses will have lower power than the main whole trial analysis but are hypothesis-generating and results will be scrutinised graphically via forest plots.

Descriptive statistics will be used to summarise the distribution of baseline variables across each of the randomisation arms. Continuous variables will be reported with means and 95% confidence intervals, if normally distributed, or medians and Interquartile Ranges (IQR) otherwise. Categorical variables will be reported using frequencies and percentages.

A Consolidated Standards of Reporting Trials (CONSORT) flow diagram will be produced, showing the frequency of participants:

- Assessed for eligibility
- Excluded prior to randomisation (and the frequency of each reason for exclusion)
- Allocated to each randomisation arm
- Receiving or not receiving their randomised treatment
- Followed-up at each protocol specified timepoints

 Lost to follow-up at each protocol specified timepoints (plus frequency of each reason for loss to follow-up)

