# 5.5. Secondary mechanistic laboratory outcome measures

- Plasma C-peptide measurements before surgery and on day one after surgery.
- Insulin measurements before surgery and day one after surgery.

- Flow cytometry assessment of metabolic dependence of leukocytes before surgery, the end of surgery, day one after surgery and on day of hospital discharge.\*
  - \* This will only be done at selected sites.

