
#### 7.3. Randomisation

Participants will be randomised on a 1:1 basis to receive either TIVA or inhalational anaesthesia by a computer generated procedure. This computerised procedure will use a minimisation algorithm to ensure balance in treatment arm allocation across the following four stratification variables, factors thought to affect outcome either

through treatment effectiveness or underlying prognosis, also permitting appropriate exploratory subgroup analyses:

- 1) Surgical speciality (musculoskeletal/intra-abdominal/thoracic/vascular/other)
- 2) Expected duration of surgery (<2hours, ≥2hours)
- 3) Cancer surgery/non-cancer surgery
- 4) Preoperative frailty (Rockwood Frailty Score) Well/Vulnerable/Frail

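### Mechanistic outcomes with a pre-surgery value: the initial arm comparison is unadjusted and its test chosen from the data, and no main analysis that uses the baseline is named

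*Protocol*

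**What the plan says.** Section 10 (Statistical considerations) sets out two stages for these outcomes.

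- First stage: "The continuous variables measuring mechanistic outcomes of glucose and metabolic profiles will initially be compared across trial arms using independent samples t-tests, or Wilcoxon" tests. A bracketed remark makes the choice depend on how the data are distributed. The primary-outcome sentence in the same paragraph has the same condition: "rank sum tests depending on the distribution of the data". Neither place names a covariate or a rule for the choice.
- Second stage, on scope: "Further comparisons across trial arms of blood glucose measures over time and the mechanistic outcomes over time". On method, the same sentence says that these "will use repeated measures analyses, a statistically efficient approach that allows all of the follow-up data collated during the study to be used". The text does not say whether the pre-surgery value is a covariate or one of the repeated outcomes, or which stage gives the main result.

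Pre-surgery values are collected. Section 5.5 lists "Plasma C-peptide measurements before surgery and on day one after surgery" and "Insulin measurements before surgery and day one after surgery". Section 7.7 confirms the timing: "Plasma C-peptide and insulin levels (ELISA assays) will be measured on the day of surgery before the induction of anaesthesia". Sections 5.5, 7.7 and 10.1 give flow cytometry a pre-induction sample and several later ones, at selected sites only. HOMA-IR (section 10.1) is derived from paired glucose and C-peptide, and both are measured before induction (sections 7.6 and 7.7).

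Section 7.3 says of allocation: "This computerised procedure will use a minimisation algorithm to ensure balance in treatment arm allocation". The four factors are surgical specialty, expected duration, cancer surgery and frailty. The section describes them as thought to affect outcome.

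**The concern.** The protocol names a method for the initial comparison, and a better one is available from data already planned. Insulin, C-peptide and HOMA-IR are likely to differ widely between patients before surgery. Section 6.3 does not exclude diabetes, section 10 makes it a subgroup, and section 7.3 does not minimise on it. A test of post-surgery values alone leaves that between-patient variation in the error term. The test also takes no account of factors that were balanced because they are expected to be prognostic.

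Two further gaps follow from the wording.

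- Choosing between a t-test and a Wilcoxon test after seeing the data lets the target change. The rank test does not estimate the mean difference on which section 10.1 sizes these outcomes.
- With two stages and no ranking between them, each outcome can yield two results, and nothing says beforehand which one counts.

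At stake are precision and a fixed target of estimation in the mechanistic part of the trial.

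**Working it through.** **Step 1. Reproduce the plan's own figure.** Section 10.1 sizes glutamine dependence with SD 7, difference 4, two-sided 5%, 90% power and 2% dropout, and states 133 patients.

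- Per arm: 2 × (1.960 + 1.282)² × 7² / 4² = 2 × 10.507 × 3.0625 = 64.4, rounded up to 65.
- Total: 130. After dropout: 130 / 0.98 = 132.7, rounded up to 133.

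The figure is reproduced exactly as a plain comparison of two means. The sizing therefore takes no credit for the baseline.

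**Step 2. Variance of the arm difference under three analyses.** Let r be the correlation between the pre-surgery and follow-up value. The protocol gives no r, so 0.3, 0.5 and 0.7 are assumed. With equal variances at both times, and relative to a post-surgery-only comparison (variance 1):

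- change score: 2(1 − r)
- baseline-adjusted (ANCOVA): 1 − r²
- ANCOVA relative to change score: (1 − r²) / (2(1 − r)) = (1 + r) / 2

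| r | ANCOVA | Change score | ANCOVA / change | Cut vs post-only | Cut vs change |
|---|---|---|---|---|---|
| 0.3 | 0.91 | 1.40 | 0.65 | 9% | 35% |
| 0.5 | 0.75 | 1.00 | 0.75 | 25% | 25% |
| 0.7 | 0.51 | 0.60 | 0.85 | 49% | 15% |

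ANCOVA has the smaller variance in every row, whichever form of the initial test is meant. Against post-only, the confidence interval width is multiplied by √(1 − r²): 0.95, 0.87, 0.71.

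**Step 3. The same gain on the glutamine scale.** Replace SD 7 by 7√(1 − r²) in step 1.

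| r | Per arm | Total incl. 2% dropout | Power at 65 evaluable per arm |
|---|---|---|---|
| none (unadjusted) | 65 | 133 | 90.3% |
| 0.3 | 59 | 121 | 92.7% |
| 0.5 | 49 | 100 | 96.4% |
| 0.7 | 33 | 68 | 99.5% |

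This applies to one follow-up time. The extra gain from the minimisation factors is not quantified, because the protocol gives nothing on their strength.

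**Step 4. What the repeated measures stage can do.** C-peptide, insulin and HOMA-IR have one follow-up value, on day one. An analysis over time is possible for them only if the pre-surgery value enters.

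- If it enters as an unconstrained outcome, the arm-by-time term with complete data is the change-score comparison. At r = 0.3 its variance (1.40) is above that of the plain post-surgery test.
- If it enters as a covariate, the result is ANCOVA (0.91 at r = 0.3).

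So the unstated detail decides whether the second stage gains or loses precision.

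**Scope.** Section 7.6 starts continuous glucose monitoring at induction. The schedule in section 7.8 also marks it in the pre-operative column of day 0, but there is in effect no pre-surgery profile to adjust for. Those measures are outside this point.

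**The case against.** The strongest reply is that the protocol does not drop the baseline. The simple tests are only what is done initially, and the next sentence commits to analysing the mechanistic outcomes over time. For three of the four outcomes that cannot be done without the pre-surgery value. This stands. A reader might infer from the first sentence that the plan discards its baselines, and the text does not support that. It supports only that the initial comparison names no covariate and that the role of the baseline in the second stage is left open.

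A second reply is that model details belong in the statistical analysis plan, to which section 10 defers and which is not at hand. That is fair for covariate lists and transformations, and the plan may already settle them. It does not remove the point, because the protocol itself names the initial test and makes its choice depend on the data.

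A third reply is that little hangs on it. Section 10.1 calls these outcomes exploratory, and planned power does not rely on adjustment. For HOMA-IR, the 45 patients per arm stated there would already give about 99.6% power for a difference of 1 SD. This limits the weight of the point, but does not argue for the less precise method when adjustment needs no further data.

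Lastly, requiring a log scale and forbidding any rank analysis would be partly preference. That is accepted, and the fix does not require either.

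**Conclusion.** The point holds as an improvement in efficiency and clarity, limited to C-peptide, insulin, HOMA-IR and flow cytometry. The initial comparison is unadjusted, its test is chosen from the data without a rule, and no main result is named.

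Baseline adjustment would cut the variance of the arm difference by 9%, 25% or 49% against post-surgery values alone, or about 35%, 25% or 15% against change scores, at r = 0.3, 0.5 or 0.7. These figures rest on assumed correlations, equal variances at the two times and a linear baseline effect. The actual size cannot be fixed from the protocol.

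Two stronger readings should be resisted.

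- A reader might infer that the results would be biased or invalid. Under randomisation the unadjusted comparison is unbiased, and ignoring the minimisation factors generally makes standard errors too large, which is conservative.
- A reader might take the 9%, 25% and 49% as the gain in all cases. They hold only if the initial test is on post-surgery values, which the protocol does not state.

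**What to change.** In section 10, or in the statistical analysis plan with the protocol wording aligned, replace the initial t-test or Wilcoxon step for these outcomes with one pre-stated main analysis per outcome.

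- C-peptide, insulin and HOMA-IR: day-one value on arm, with the pre-surgery value and the four minimisation factors as covariates.
- Flow cytometry: a repeated-measures model of the post-surgery values on arm, time and their interaction, with the pre-surgery value and the same factors as covariates. Name the time point at which the arm difference is the main result.
- Fix any transformation for each outcome before the data are seen.
- Keep a rank-based analysis only as a pre-stated sensitivity analysis.
- State how a missing pre-surgery value is handled, so that adjustment does not drop randomised patients.

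The cost is wording, with no new samples or visits. By the levels in section 7.3 the covariates use nine degrees of freedom (specialty 4, duration 1, cancer 1, frailty 2, baseline 1), which 130 evaluable patients can carry. Because flow cytometry runs only at selected sites, a rule for merging sparse specialty levels should be set in advance.
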